10.7 Efficacy Analysis

The efficacy endpoints are the following:

Primary endpoint

Time to solid food tolerance

Secondary endpoints

- Solid food tolerance at 48 hours, 72 hours, and 96 hours after the SFISD and at discharge
- Time to medically indicated discharge
- Length of stay in the hospital
- Length of stay in the ICU for patients admitted to the ICU
- Re-hospitalization for AP by Day 30
- Change in severity of AP by CTSI score from screening to Day 30
- Development of pancreatic necrosis ≥30% and >50%
- The persistence of SIRS ≥48 hours after the SFISD
- Incidence, severity, and duration of organ failure
- Mortality by Day 30
- Change in pain score and opioid use

Exploratory endpoints

- Development of infected pancreatic necrosis
- Development of sepsis
- Hospital procedures for the management of pancreatic necrosis
- Change in GCSI-DD score
- Change in albumin
- Change in ANC/ALC ratio and IL-6 levels
- Change in urine NGAL

Time to solid food tolerance is the number of hours from the date and time of the SFISD for the patient to the first date and time the patient receives a solid meal that is tolerated, which is defined as eating \geq 50% of a low fat, \geq 500-calorie solid meal without an increase in abdominal pain or vomiting in the two hours after completing the meal.

Time to solid food tolerance for patients who could not tolerate solid food during the study will be censored on the latest date and time of food tolerance assessment.

Time-to-event endpoints will be summarized using Kaplan-Meier analyses. The medians and quartiles of time-to-events will be summarized. Time to solid food tolerance will be compared between each treatment groups and the placebo group using the stratified log-rank test as the primary analysis. The tests will be at an alpha level of 0.05 without multiplicity adjustment. The stratification variables will include gender (male vs. female) and disease severity status (higher

risk for organ failure defined by the presence of both a HCT \geq 44% for men, or \geq 40% for women, and a PaO₂/FiO₂ \leq 360 before randomization (Figure 4).

In addition, the hazard ratio (HR) and the 95% CI will be estimated using a Cox proportional-hazard model with treatment group as the independent variable and stratified by the same randomization stratification factors as used for the log-rank test.

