8.1.2 Significance Level and Confidence Interval

The statistical tests will be performed as two-sided with significance level of 5% unless specified otherwise. The confidence intervals will be determined with a confidence level of 95%.

Protocol CM4620-203 CONFIDENTIAL Page 11 of 31

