8.6 Primary Endpoint Analysis

8.6.1 Generalized Multiple Comparisons and Modelling (gMCP-Mod)

The primary objective of this study is to demonstrate a dose-response effect of Auxora compared to placebo of the primary endpoint time to solid food tolerance through Day 30. To demonstrate the dose-response relationship between treatment with Auxora compared to placebo for the primary endpoint, the primary analysis will be based on a generalized Multiple Comparisons and Modeling (gMCP-Mod) analysis [Bretz et al., 2005; Pinheiro et al., 2014]. This analysis tests for a dose-response relationship, allowing for uncertainty in the dose-response relationship through inclusion of contrasts from multiple pre-specified candidate models assessing dose-response.

This is accomplished by decoupling the dose-response model from the expected response through the use of an ANOVA-style parameterization of the dose-response parameter. For the time-to-event endpoint used in this study, a stratified Cox regression of the time to solid food tolerance at each dose level will be used, stratified by the CRF recorded sex (male or female) and then by risk for organ failure based on CRF data in the sex subgroups (higher or lower). After this first step, the mean estimates of log hazard ratio from the Cox regression model and the corresponding covariance matrix, both of which are on the log scale, will then be used during the rest of the gMCP-Mod procedure. Point estimates from the selected models will be displayed on the ratio scale in all statistical outputs.

The gMCP-Mod (Pinheiro et al., 2014) will be employed in a three-step approach in the manner described below:

Protocol CM4620-203 CONFIDENTIAL Page 14 of 31

• Step 1: Conventional Step – Hazard Ratio Between Each Dose Versus Placebo

The data are analyzed using stratified Cox regression to obtain treatment effects and corresponding variance covariance matrix. The Cox regression will be stratified by sex (male or female) and the risk for organ failure (higher or lower).

The estimated treatment hazard ratio and the associated 95% confidence intervals will be presented for the treatment contrast of each dose of Auxora versus placebo

• Step 2: Proof-of-concept Step – Candidate Models and Multiple Testing Procedure

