The null hypothesis of flat dose-response relationship as compared to placebo for the primary efficacy endpoint will be tested at a significance level of one-sided 15% against the alternative hypothesis of a non-constant dose-response curve using a multiple contrast test as described in the gMCP-Mod methodology (Pinheiro et al., 2014). The contrast test statistic is a linear combination of the optimal contrast coefficients corresponding to the candidate dose-response curve with the hazard ratio at each individual dose obtained from Step 1 (conventional step).

The contrast coefficients are chosen to maximize the power to detect pre-specified candidate models. There are two candidate models that will be considered for the primary analysis with the optimal contrasts shown in following table. These optimal contrasts will be updated using the expected model means from the candidate set of the two models and the estimated variance-covariance matrix from the collected data. The updated contrast coefficients will be described in the final CSR.

The optimal contrast based on Candidate models for Auxora dose for log(Hazard Ratio):

Model	Contrast Coefficients for Dose					
Dose	0.5 mg/kg	1.0 mg/kg	2.0 mg/kg			
Emax	0.508	0.588	0.629			
sigEmax	-0.611	0.488	0.623			

Note: Candidate model of Emax model is based on the assumption of parameter of ED50=0.026 mg/kg. Candidate model of sigEmax mode is based on the assumption of parameters of ED50=0.707 mg/kg and h=6.34.

The proof of concept (PoC) is established if at least one dose-response model is statistically significant, thereby rejecting the null hypothesis of a flat dose-response curve and indicating a benefit of Auxora over placebo.

The global test decision is based on the maximum of the contrast test statistics. A critical value q controlling the type I error rate can be derived from the fact that the contrast test statistics approximately follow a multivariate normal distribution and that their maximum

Protocol CM4620-203 CONFIDENTIAL Page 15 of 31

follows the distribution of the maximum of a multivariate normal distribution. If the maximum contrast test statistic exceeds the critical value q, the overall null hypothesis of a flat dose-response curve is rejected, and one proceeds to characterize the dose-response efficacy relationship.

For each candidate dose-response curve, the test statistics and corresponding adjusted p-values will be presented.

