Once proof of concept has been established, then subsequently, it will be tested whether at least one dose of Auxora achieves time to solid food tolerance superior to placebo (i.e., the maximum anticipated effect of Auxora for achieving the primary endpoint, based on the best fitting monotonic dose-response model).

• Step 3: Dose-finding Step – Dose-Response Model Fitting

Once the significance of a dose-response signal is established, the dose-response profile and the target dose can be estimated using the best-fitting dose-response model. All significant dose-response models will be re-fitted to the data without any parameter assumptions to generate a set of new estimates of the model parameters from the data. The final dose-response model will be obtained via the model with the smallest Akaike Information Criterion (AIC) (the smaller the AIC value the better the model fit). Estimates for the dose groups will be calculated and will be based on the final dose-response model.

The dose-response curve estimate with the model-based two-sided 95% confidence interval will be presented graphically. In addition, the plot will include the mean responses from the Cox Regression and the associated 95% confidence intervals for each of the studied dose groups.

The target dose(s) suggested by gMCP-Mod based on time to solid food tolerance serves as an important consideration in dose selection. However, the final dose selection will be determined based on the following:

- Efficacy of doses based on the totality of efficacy data
- Safety endpoints including AEs, and SAEs

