8.6.2 Definition of Estimand

CalciMedica Inc.

Time to solid food tolerance through the Day 30 is the primary endpoint.

The primary estimand corresponding to the primary endpoint is defined as:

- 1. Treatment: 2.0 mg/kg (1.25 mL/kg), 1.0 mg/kg (0.625 mL/kg), or 0.5 mg/kg (0.3125 mL/kg), every 24 hours (±1 hour) for three consecutive days for a total of three infusions.
- 2. Population: Patients with Acute Pancreatitis and Accompanying Systemic Inflammatory Response Syndrome
- 3. Variable: Time to solid food tolerance as the number of hours from the date and time of the SFISD for the patient to the first date and time the patient receives a solid meal that is

Protocol CM4620-203 CONFIDENTIAL Page 16 of 31

tolerated, which is defined as eating \geq 50% of a low fat, \geq 500-calorie solid meal without an increase in abdominal pain or vomiting within the two hours of mealtime.

4. Population level summary: hazard ratio using stratified Cox Regression

Intercurrent events under consideration: 1) prohibited immunosuppressive medications or immunotherapies, 2) treatment discontinuation, and 3) death.

The null and alternative hypotheses are:

- (1) Null hypothesis H0: Time to solid food tolerance curves are the same between Auxora and placebo
- (2) Alternative hypothesis H1: Time to solid food tolerance curves are different between Auxora and placebo

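### Protocol and SAP name different primary tests, and the SAP reads a one-sided 15% dose-response signal as benefit over placebo

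*SAP*

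**What the plan says.** Protocol 10.7 compares time to solid food tolerance between each dose and placebo "using the stratified log-rank test as the primary analysis". It adds: "The tests will be at an alpha level of 0.05 without multiplicity adjustment". That sentence does not say whether the tests are one- or two-sided.

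SAP 8.6.1 says that "the primary analysis will be based on a generalized Multiple Comparisons and Modeling (gMCP-Mod) analysis". In Step 2 the flat-curve null "will be tested at a significance level of one-sided 15% against the alternative hypothesis of a non-constant dose-response curve". One significant candidate model is enough, "thereby rejecting the null hypothesis of a flat dose-response curve and indicating a benefit of Auxora over placebo". Afterwards "it will be tested whether at least one dose of Auxora achieves time to solid food tolerance superior to placebo". A parenthesis ties this step to the largest effect expected under the best-fitting monotonic model, but no test statistic or level is given.

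Four other places bear on the same decision:

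- SAP 8.6.5 keeps the stratified log-rank comparison, as a supplementary analysis.
- SAP 8.6.2 sets a null of equal curves against the alternative "Time to solid food tolerance curves are different between Auxora and placebo".
- SAP 13, which records changes from the protocol's planned analysis, has one entry, on length of stay in the ICU.
- SAP 4 repeats the 86% power from Protocol 10.2 but leaves out that it refers to a log-rank test. Neither document gives power for gMCP-Mod.

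**The concern.** Two rules are each called primary for the same endpoint, and they differ in statistic, level and null hypothesis. The same data could be a primary success under the SAP and a primary failure for every dose under the protocol. If this is not settled before unblinding, the rule that decides could be chosen with the result in view.

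The second problem is what a pass is said to mean. The contrast test detects a curve that is not flat in the direction of a candidate shape. The SAP goes directly from there to benefit over placebo, before its own superiority step. In the printed sigEmax contrast, 0.5 mg/kg has weight -0.611, so a poor result at that dose raises the test statistic. A pass can therefore come from one dose doing badly.

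**Working it through.** HR above 1 means faster tolerance on Auxora.

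**The plan's own figures**
- 45% vs 20%, 54 per arm, two-sided 0.05: (0.25√54 − 1.96√(2·0.325·0.675)) / √(0.45·0.55 + 0.20·0.80) = (1.837 − 1.298)/0.638 = 0.844, so power is 80.1%. This matches the stated 80%.
- Medians 72 vs 144 h give HR 2 under exponential times. Schoenfeld power is Φ(½√D·ln 2 − 1.96). With D = 108 (everyone has the event) it is 95.0%; 86% needs D = 77 (84 by Freedman's form). No event count is given, so the 86% can be neither confirmed nor refuted. It is a pairwise log-rank figure in either case.

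**Inputs for comparing the rules**
- Events per arm (assumption): 52. With a placebo median of 144 h and 720 h of follow-up, 54 × (1 − 2⁻⁵) = 52.3.
- Candidate shapes at 0.5, 1.0 and 2.0 mg/kg (SAP 8.6.1): Emax with ED50 0.026 gives 0.951, 0.975, 0.987; sigEmax with ED50 0.707 and h 6.34 gives 0.100, 0.900, 0.999.
- Covariance of the log HRs: S = diag(1/d_i) + 1/d_0. Optimal contrasts are proportional to S⁻¹ times the shape.
- Equal events give contrasts 0.528/0.585/0.615 and −0.530/0.531/0.661, correlation 0.661, and a one-sided 15% critical value of 1.307.
- Sensitivity case: a placebo-to-active event ratio of 2:3 gives 0.509/0.588/0.629 and −0.611/0.488/0.623, the printed table to within 0.001, with critical value 1.323. The table fixes only this ratio, not the counts. I use 27 and 40.5.
- Log-rank success: z > 1.96 favouring Auxora for at least one dose (two-sided 0.05 assumed).

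**Window of disagreement for an observed HR common to all doses**
- SAP limit: exp(1.307·√(1/52 + 1/156)) = exp(0.209) = 1.23. There the pooled 95% CI is 0.90-1.69 and each pairwise two-sided p is 0.29.
- Protocol limit: exp(1.96·√(2/52)) = exp(0.384) = 1.47.
- With 27/40.5 events the window is 1.33-1.63; with 36/54 it is 1.28-1.52.

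**No effect at any dose** (1,000,000 normal draws)
- SAP test passes: 15.0%.
- Any favourable log-rank result: 5.9-6.3%.
- SAP test passes with no dose significant: about 9.6%.

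**0.5 mg/kg at HR 0.7, other doses at HR 1**
- 27/40.5 events: the sigEmax contrast has mean (−0.611)·ln 0.7 = 0.218 and SD √(1/40.5 + 0.5²/27) = 0.184, so its expected z is 1.18. The chance of exceeding 1.323 is Φ(−0.14), about 44%; simulation of the full test gives about 45%.
- 52 events per arm: 0.189/0.166 = 1.14 against 1.307, about 43%.
- Printed contrasts held fixed, 38.5 to 54 events in every arm: 45-54%.

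**SAP test passes and no dose is log-rank significant, 52 events per arm**

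| Top-dose HR | Emax shape | sigEmax shape |
|---|---|---|
| 1.5 | 13.0% | 25.4% |
| 1.75 | 3.7% | 9.4% |
| 2 | 0.6% | 2.3% |

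A patient-level check at HR 1.5 (3,000 trials, stratified Cox and log-rank, contrasts updated from the data, 720 h) gave 13.9% and 28.1%.

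**The case against.** This is a Phase 2 study whose first primary objective is dose response, and Protocol 10.1 describes the approach as partly exploratory. A generous one-sided level is a normal choice for a dose-response signal, and the contrast test does hold its 15% when no dose has an effect. SAP 8.6.1 reports each dose's HR with a 95% CI, 8.6.5 keeps the log-rank test, and dose selection rests on all efficacy and safety data. A reader would see a result in which only the contrast test passed. All of this stands. It does not settle which test is primary, or justify calling a pass benefit.

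Four stronger readings are tempting, and the documents do not support them:

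- *The SAP contains a third decision rule.* SAP 8.6.2 states hypotheses without a test or level. SAP 8.1.2 says "The statistical tests will be performed as two-sided with significance level of 5% unless specified otherwise", and Step 2 does specify otherwise. What remains is a mismatch: 8.6.2 is non-directional and is not the flat-curve null.
- *The follow-on superiority step is empty.* Its text points to a model-based comparison. It is incomplete.
- *The trial is underpowered or the 86% is wrong.* The events behind that figure are not given, and power of the contrast test at HR 2 is about 98% or higher in both event scenarios.
- *Phase 2a makes disagreement likely.* The high-dose median (78.5 vs 100 h) implies HR 1.27 under exponential times, where disagreement is about 21% / 32% (Emax / sigEmax). The same sentence of Protocol 1.5.2 gives 57 h for the low-dose regimen, HR 1.75, where it is 3.7% / 9.4%. These medians come from 6, 8 and 7 patients, so neither is an estimate to rely on.

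**Conclusion.** Wrong as written, on the text alone: two different primary tests, an unlisted change, hypotheses that do not match the test, and a benefit statement that does not follow from it. SHOULD be corrected.

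The practical size depends on the true effect. Disagreement between the rules is negligible to small at the design HR of 2, and material at HR 1.5 or when there is no effect. The figures rest on assumed event counts, exponential times and a normal approximation. The SAP will update its contrasts from the data, so limits and rates will shift somewhat. The SAP cites protocol version 4, and the version of the supplied protocol cannot be confirmed against it. The 15% level for a dose-response signal is not in dispute.

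**What to change.** Before unblinding:

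1. Name the same primary analysis, level and sidedness in Protocol 10.7 and SAP 8.6.1.
2. In Step 2 of SAP 8.6.1, replace the benefit wording with a statement that a dose-response signal was detected. Let any benefit statement for a dose rest on the follow-on superiority step.
3. Give that step a test statistic and a level. It may be model-based, as its text suggests, or the log-rank test of 8.6.5; the choice is the sponsor's.
4. Rewrite the hypotheses in SAP 8.6.2 to match the flat dose-response null and the follow-on test.
5. List the change of primary test and level, with its rationale, in SAP 13.
6. In SAP 4, label the 86% as pairwise log-rank power and add gMCP-Mod power under both candidate models.

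The cost is text changes, one power calculation and a more modest conclusion when only the contrast test passes. Sample size, data collection and the 15% level stay as they are.

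The choice in item 3 is a real trade-off. If the log-rank test at two-sided 0.05 is chosen, the power for a benefit statement at HR 1.5 (Emax / sigEmax) falls from 90.2% / 92.6% to 77.2% / 67.1% with 52 events per arm, and from 75.1% / 84.0% to 57.0% / 47.9% with 27/40.5. At HR 2 it stays at 99.2% / 97.7% and 92.7% / 87.3%.

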8.6.2 Definition of Estimand

CalciMedica Inc.

Time to solid food tolerance through the Day 30 is the primary endpoint.

The primary estimand corresponding to the primary endpoint is defined as:

- 1. Treatment: 2.0 mg/kg (1.25 mL/kg), 1.0 mg/kg (0.625 mL/kg), or 0.5 mg/kg (0.3125 mL/kg), every 24 hours (±1 hour) for three consecutive days for a total of three infusions.
- 2. Population: Patients with Acute Pancreatitis and Accompanying Systemic Inflammatory Response Syndrome
- 3. Variable: Time to solid food tolerance as the number of hours from the date and time of the SFISD for the patient to the first date and time the patient receives a solid meal that is

Protocol CM4620-203 CONFIDENTIAL Page 16 of 31

tolerated, which is defined as eating \geq 50% of a low fat, \geq 500-calorie solid meal without an increase in abdominal pain or vomiting within the two hours of mealtime.

4. Population level summary: hazard ratio using stratified Cox Regression

Intercurrent events under consideration: 1) prohibited immunosuppressive medications or immunotherapies, 2) treatment discontinuation, and 3) death.

The null and alternative hypotheses are:

- (1) Null hypothesis H0: Time to solid food tolerance curves are the same between Auxora and placebo
- (2) Alternative hypothesis H1: Time to solid food tolerance curves are different between Auxora and placebo

8.6.3 Main Analytical Approach

Time to solid food tolerance through Day 30 visit will be analyzed based on the Generalized Multiple Comparison Modelling (gMCP-Mod) approach described in Session 8.6.1.

Time to solid food tolerance is defined as the number of hours from the date and time of the SFISD for the patient to the first date and time the patient receives a solid meal that is tolerated. If the mealtime was not recorded, the mealtime will be estimated using the middle time of the meal serving interval.

Tolerating a solid meal is defined as eating \geq 50% of a low fat, \geq 500-calorie solid meal without an increase in abdominal pain or vomiting within the two hours of mealtime. In addition, to meet the definition, all subsequent meals during the hospitalization should not show an increase in abdominal pain or vomiting within the two hours of mealtime. If a procedure that could impact food tolerance is performed after a solid meal is initially tolerated that results in subsequent meals not being tolerated, the time of the initial tolerated meal will be considered in the calculation of the time to solid food tolerance. The procedures that impact food tolerance and/or its assessment are defined as (1) a procedure that requires a period of nil by mouth (2) a procedure and/or treatment that causes gastrointestinal dysfunction e.g., cholecystectomy, necrosectomy. The procedures performed after the initial food tolerance will be reviewed before the database lock to identify the procedures that could impact the time to the tolerated solid food. If the subject was not discharged from the hospital during the study and did not tolerate solid food, the time to solid food tolerance will be censored at the latest date and time of the hospital stay.

If a patient is discharged home without tolerating solid food, the daily record of the modified American Neurogastroenterology and Motility Society Gastrointestinal Cardinal Symptom Index Daily Diary (mGCSI-DD) at or after hospital discharge will be used in the calculation of the time to solid food tolerance. The patients who did not tolerate solid food while hospitalized will be considered as tolerating solid food at or after hospital discharge at 8am on the first of three consecutive days where the following 4 criteria are met for the mGCSI-DD:

Protocol CM4620-203 CONFIDENTIAL Page 17 of 31

- none for vomiting
- none or mild for nausea
- none or mild for not being able to finish a normal sized meal for a healthy person
- none or mild for abdominal pain

If the mGCSI-DD is not available at or after discharge in a patient discharged home without tolerating a solid meal, the time to solid food will be censored at 168 hours.

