8.11 Discharge Date

The time and date of discharge will be recorded as well as if the patient meets criteria for medically indicated discharge. All patients will be trained to complete the mGCSI-DD and will complete the mGCSI-DD before leaving the hospital. If patients are discharged on Days 25-29, they may complete the Day 30 assessments on the day of discharge. Following discharge, the Investigator or designee should contact patient by telephone once per week to confirm diary completion and patient agrees to return for Day 30 visit.

If a patient is admitted to a hospital following discharge but prior to Day 30 visit, Investigator will report the reason for the hospitalization as per serious adverse event reporting guidelines (See Section 9.2 and Section 9.7). As the patient is still within the study period, investigators or designee should resume collection of study procedures as per Schedule of Events (See Appendix 8). If patient is not admitted to the hospital where the study is being conducted, investigators are asked to record any procedures (i.e., invasive mechanical ventilation) received while patient was admitted during the study period within an unscheduled procedures form in the eCRF.

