8.12.10 Modified ANMS GCSI-Daily Diary (mGCSI-DD)

The ANMS GCSI Daily Diary was designed to assess gastrointestinal symptoms associated with idiopathic and diabetic gastroparesis. It has been shown to be a reliable tool to evaluate dysmotility in patients with AP (Ma 2016). It will be used to assess gastrointestinal symptoms associated with AP in an exploratory manner. The mGCSI-DD has a 24-hour recall; thus, all items are designed to be self-administered on a daily basis.

The patient training for completing the daily diary is provided by the PI or appropriately trained delegate. Patients should understand their disorder: AP, where there is an abnormally delayed emptying of food from the stomach because of inflammation in the pancreas. The mGCSI-DD recording sheet and instructions are reviewed with the patient prior to the patient starting the recording of daily symptoms in the diary. The symptom severity response items are reviewed: "For each symptom listed below, please mark with an X the box that best describes the worst severity of each symptom during the past 24 hours. The next question asks you to record the number of times vomiting occurred in the last 24 hours. Please record the number of vomits (throwing up with food or liquid coming out) that occurred in the last 24 hours. Record zero, if you have not vomited during the past 24 hours. If you vomited, write down the number of all vomits. If you vomited once, record one. If you vomited three times during the day, record three. If you vomited three times, whether it was during the same trip to the bathroom or three separate trips, record three as the number of episodes of vomiting."

Patients discharged before Day 25 will complete the daily diary on the day of discharge, and then after discharge, daily at bedtime until the Day 30 visit.

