8.7 Secondary Endpoint Analyses

8.7.1 Percentage of Patients who Tolerated Solid Food at 48, 72, and 96 Hours from the SFISD and at Discharge

Solid food tolerance will be calculated using the main analytical approach as described in Section 8.6.3.

If the time to first solid food tolerance \leq 48 hours then solid food tolerance at 48, 72 and 96 hours are all yes.

If the time to first solid food tolerance >48 and \leq 72 hours, then solid food tolerance at 72 and 96 hours are all yes and solid food tolerance at 48 hours is no.

If the time to first solid food tolerance >72 and <96 hours, then solid food tolerance at 96 hours is yes and solid food tolerance at 48 and 72 hours are all no.

Protocol CM4620-203 CONFIDENTIAL Page 18 of 31

If the time to first solid food tolerance > 96 hours or the patient never tolerates the solid food during the study then solid food tolerance at 48, 72, and 96 hours are all no.

If the time to first solid food tolerance ≤time to hospital discharge, solid food tolerance at discharge is yes, otherwise, solid food tolerance at discharge is no. If a patient was not discharged from the hospital before end of study, solid food tolerance at the end of study is no.

If it is unknown if solid food has been tolerated at a specific time point (time to first solid food tolerance is censored before the specific time point), the solid food tolerance will be imputed as no.

The proportion and 95% CI of patients who tolerated solid food at 48, 72, and 96 hours from the SFISD, at discharge, and at the end of the study will be displayed using a Clopper-Pearson interval and will be compared between each Auxora treatment group and placebo group using a Cochran-Mantel-Haenszel test stratified by the eCRF recorded sex (male or female) and the risk for organ failure (higher or lower) based on eCRF data. Prohibited immunosuppressive medications or immunotherapies and treatment discontinuation will be ignored (treatment policy strategy).

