8.7.2 Time to Medically Indicated Discharge

The time to medically indicated discharge is the number of days from the SFISD to the first date of meeting the criteria defining medically indicated discharge:

- the patient tolerates solid food, as defined by the main analytical approach; and
- abdominal pain is controlled or resolved, which will be defined by a reduction in pain, as assessed by the PNRS scale, of ≥50% from the peak level in the first 24 hours and no use of opioids; and
- there is no clinical evidence of an infection requiring continued hospitalization.

In patients who do not meet the criteria for medically indicated discharge when discharged from the hospital, the time to medically indicated discharge will be defined as 8am on the first of three consecutive days where the 4 criteria are met for the mGCSI-DD as defined in 8.6.3. If a patient is discharged not meeting the criteria for medically indicated discharged and does not meet criteria for the mGCSI-DD or has not completed the mGCSI-DD, the time to medically indicated discharge will be censored at 168 hours. If the patient dies while hospitalized, the time to medically indicated discharge will be censored at Day 30.

The time to medically indicated discharge will be summarized using Kaplan-Meier analyses. The medians and quartiles of time-to-events will be summarized for each study group. The time to medically indicated discharge will be compared between each Auxora treatment group and placebo group using stratified log-rank test stratified by sex (male or female) and the risk for organ failure (higher or lower). Prohibited immunosuppressive medications or immunotherapies and treatment discontinuation will be ignored (treatment policy strategy).

Protocol CM4620-203 CONFIDENTIAL Page 19 of 31

The proportion and 95% CI of patients who meet the medical discharge criteria by the 96-hour visit and the date of discharge will be displayed using a Clopper-Pearson interval and will be compared between each Auxora treatment group and placebo group using a Cochran-Mantel-Haenszel test stratified by the eCRF recorded sex (male or female) and the risk for organ failure (higher or lower) based on eCRF data. Prohibited immunosuppressive medications or immunotherapies and treatment discontinuation will be ignored (treatment policy strategy).

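### Diary-based times in SAP 8.6.3 let patients sent home without tolerating solid food be scored in SAP 8.7.1 as tolerating it at discharge

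*SAP*

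**What the plan says.** SAP 8.6.3 derives time to solid food tolerance from meals eaten in hospital and adds a rule for patients who leave without a tolerated meal. "If a patient is discharged home without tolerating solid food", the daily mGCSI-DD record "at or after hospital discharge will be used in the calculation of the time to solid food tolerance". Such patients "will be considered as tolerating solid food at or after hospital discharge at 8am on the first of three consecutive days" on which four diary criteria hold: no vomiting, and at most mild nausea, difficulty finishing a meal and abdominal pain.

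The protocol fixes when the first usable entry is made. Section 8.12.10 states: "Patients discharged before Day 25 will complete the daily diary on the day of discharge". Section 8.11 adds that all patients "will complete the mGCSI-DD before leaving the hospital". Section 8.12.10 also says: "The mGCSI-DD has a 24-hour recall".

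SAP 8.7.1 takes its tolerance times from 8.6.3. If the time is no later than the time to hospital discharge, "solid food tolerance at discharge is yes, otherwise, solid food tolerance at discharge is no". Nothing exempts patients whose time comes from the diary.

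SAP 8.7.2 reuses the device. For patients who do not meet the discharge criteria when they leave, "the time to medically indicated discharge will be defined as 8am on the first of three consecutive days" that satisfy the same diary criteria. It also reports the proportion meeting the criteria by the 96-hour visit and by the date of discharge.

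**The concern.** The diary rule applies only to patients who failed the meal-based definition in hospital. For them, tolerance at discharge should be no by construction. Yet the discharge-day entry can open the run of three qualifying days, and the fixed clock time then puts the event at or before the moment the patient left. The at-discharge comparison in 8.7.1 reads that as success.

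The scenario is plausible. With 24-hour recall, an entry made before leaving describes inpatient hours. The diary criteria accept mild symptoms, whereas the meal definition requires at least half of a meal of 500 calories or more with no increase in pain. The same hours can fail one definition and pass the other.

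At stake are the secondary endpoint of tolerance at discharge, in some cases the 48, 72 and 96 hour rates, and the related proportion in 8.7.2.

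**Working it through.** No figure in the plan depends on this rule, so there is none to reproduce. The check applies the written rules to clock times.

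**Inputs from the documents.** The 8am time on the first of three qualifying days (SAP 8.6.3); a diary entry on the discharge day, made in hospital (Protocol 8.11 and 8.12.10); the scoring rule, yes if time to tolerance ≤ time to discharge (SAP 8.7.1); hours counted from the start of first infusion, SFISD (SAP 8.1.4.2).

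**Assumed for illustration.** SFISD on Day 1 at 10:00; no tolerated meal in hospital; discharge on Day 5; diary criteria met on Days 5, 6 and 7.

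**Formulas.**
- Assigned time as written = Day 5 08:00 − Day 1 10:00 = 94 h.
- Floored time = the later of 94 h and the discharge time.
- At discharge = yes if the time used ≤ discharge time.
- At 96 h = yes if the time used is below 96 h.

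| Discharge, Day 5 | Discharge (h) | Discharge minus 94 h | At discharge, as written | At discharge, floored | At 96 h, as written | At 96 h, floored |
|---|---|---|---|---|---|---|
| 07:00 | 93 | −1 | no | no | yes | yes |
| 08:00 | 94 | 0 | yes | yes | yes | yes |
| 11:00 | 97 | 3 | yes | yes | yes | no |
| 14:00 | 100 | 6 | yes | yes | yes | no |
| 18:00 | 104 | 10 | yes | yes | yes | no |
| 23:59 | 109.98 | 15.98 | yes | yes | yes | no |

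**Reading the table.**
1. Every discharge at or after 08:00 is scored yes at discharge. Only the 07:00 case gives no.
2. Flooring the time at discharge leaves that column unchanged. In the 14:00 case the floored time is 100 h, and 100 ≤ 100 is still yes.
3. In the last four rows the patient is still in hospital at 96 h without a tolerated meal, yet is scored yes at 96 h. Flooring does correct this. In the first two rows the patient has already left by 96 h, so a diary-based yes there is what the rule intends.
4. The 48, 72 and 96 hour cut-offs are whole days after SFISD, so each falls at the clock time of SFISD. The error in item 3 therefore needs an SFISD clock time between 8am and the discharge clock time, with discharge on the calendar day of that cut-off.
5. If the first qualifying day is the day after discharge, the assigned time is Day 6 08:00 = 118 h. That exceeds every discharge time in the table, and the score is correctly no.

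**Size.** With 54 patients per group, one affected patient moves that group's at-discharge rate by 1/54 = 1.9 percentage points. As an assumed range, 0 to 3 affected patients in a group give 0 to 3/54 = 5.6 points.

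**Section 8.7.2.** This endpoint is counted in days to a first date. A patient who leaves without meeting the criteria, but whose discharge-day diary is the first qualifying one, gets the discharge date as the date of meeting them. Counted by date, that patient enters the proportion meeting criteria by the date of discharge, whether or not the clock time is floored.

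**The case against.** The strongest reply is that 8.6.3 itself speaks of tolerance at or after hospital discharge, which may be meant to exclude an earlier time. That reading is fair, and the conflict with a fixed 8am on the discharge day may be a drafting ambiguity. It does not settle the matter: the SAP states no floor, and a floor still returns yes under the ≤ rule.

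Second, the sensitivity analysis in 8.6.4 censors these patients at 168 hours, and supplementary analysis 2 in 8.6.5 does the same for the log-rank test. That protects the reading of the primary endpoint, but 8.7.1 uses the main approach only.

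Third, the protocol (3.1 and 5.3) makes tolerance of solid food a condition of recommended discharge, which should keep the number of such patients low, and the rule is the same in every group. Both points stand. They limit the size of the error without making the score right.

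Fourth, 8.7.2 also covers patients who tolerated food but failed on pain or infection, so the premise does not carry over word for word. The parallel contradiction remains: a patient who left without meeting the criteria can be counted as meeting them by the date of discharge.

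A reader might also infer that 8am is wrong on later days because it precedes the bedtime entry. The documents do not support this. With 24-hour recall, 8am lies inside the period that a bedtime entry describes, and a fixed clock time is an acceptable convention. Nor do they show that a meal record must contradict the 8am time: a qualifying diary excludes vomiting and allows at most mild symptoms, and no failed meal after 8am is required.

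**Conclusion.** The point holds for the scoring of tolerance at discharge in SAP 8.7.1. As written, the plan can return yes for a patient whom 8.6.3 has already classed as discharged without tolerating food. Three conditions are needed: no tolerated meal in hospital, diary criteria met on the discharge day and the next two days, and discharge at or after 8am. It does not affect every patient sent home without tolerance.

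The assigned time precedes discharge by 0 to 16 hours. A wrong yes at 48, 72 or 96 hours follows only when that cut-off falls in the same gap. The number of affected patients is not in the documents, so the effect on the rates cannot be computed beyond 1.9 percentage points per patient per group.

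A reader might infer that the primary result is compromised. The documents do not support that: affected event times shift by at most 16 hours, the influence on the Cox analysis is likely small, and 8.6.4 tests the diary assumption. This is a secondary-endpoint error that should be corrected.

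**What to change.** - **SAP 8.7.1:** score tolerance at discharge from in-hospital meal records only, so that a diary-based time never counts as yes at discharge. This is the change that cures the misclassification.
- **SAP 8.6.3:** state that a diary-based time is the later of 8am on the first qualifying day and the recorded discharge date and time. This corrects the 48, 72 and 96 hour scores.
- **SAP 8.7.2:** apply the same floor, and do not count patients who met the criteria only through the diary in the proportion meeting them by the date of discharge.

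The cost is a few sentences in three sections. No new data are needed: meal outcomes are recorded under Protocol 5.2, and discharge date and time under Protocol 8.11. A few event times move later by up to 16 hours, and the at-discharge rate may fall slightly.
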